8.3 Evaluating Adverse Events

An investigator who is a qualified physician will evaluate all adverse events according to the NCI Common Terminology for Adverse Events (CTCAE), version 4.0. Any adverse event which changes CTCAE grade over the course of a given episode will have each change of grade recorded on the adverse event case report forms/worksheets.

All adverse events regardless of CTCAE grade must also be evaluated for seriousness.

8.4 **Recording of Adverse Events**

At each contact with the subject, the investigator must seek information on adverse events by specific questioning and, as appropriate, by examination. Information on all adverse events should be recorded immediately in the source document, and also in the appropriate adverse event module of the case report form (CRF). All clearly related signs, symptoms, and abnormal diagnostic procedures results should recorded in the source document, though should be grouped under one diagnosis.

All adverse events occurring during the study period must be recorded. The clinical course of each event should be followed until resolution, stabilization, or until it has been determined that the study treatment or participation is not the cause. Serious adverse events that are still ongoing at the end of the study period must be followed up to determine the final outcome. Any serious adverse event that occurs after the study period and is considered to be possibly related to the study treatment or study participation should be recorded and reported immediately.

8.5 Reporting of Serious Adverse Events

8.5.1 IRB Notification by Sponsor-Investigator

Reports of all events (including follow-up information) that meet the definition of an unanticipated problem posing risk to subjects or others must be submitted to the IRB within one week (5 business days) following the occurrence of the unanticipated problem or the principal investigator's acquiring knowledge of the unanticipated problem in accordance with IRB policy. Additionally, the sponsor-investigator will submit a summary of all Unanticipated problems that occurred since the beginning of the study at the time of continuing review. Copies of each report and documentation of IRB notification and receipt will be kept in the Regulatory binder.

8.5.2 SAE Reporting to Incyte

The Principal Investigator (PI) must report all Serious Adverse Events (SAEs) to Incyte within 24 hours of learning of an event, regardless of the PIs causality assessment. This notification should be provided on a completed Serious Adverse Event (SAE) form. SAE reporting for each subject begins the day the informed consent is signed by the patient and within 30 days after subject has completed or discontinued from the study or has taken last dose of the study drug, or as described in the protocol.

SAEs, occurring using Incyte Study drug, are reported in accordance with the effective protocol. SAEs occurring with any other commercial drug are reported to the manufacturer of that drug in accordance with regulations and protocol.

Initial SAEs and/or subsequent follow-up reports should be reported via email to [contact] or fax [name]. SAE reports should be for a single subject. SAE forms should be sent with a cover sheet and any additional attachments.

All adverse event information is reported to Incyte on the Principal

Investigator's/Institution's Adverse Event Report Form, or a CIOMS-I or MedWatch Form FDA 3500A, or on an Adverse Event Report Form which may be provided by Incyte upon request. The Principal Investigator does not provide medical records (e.g., discharge summary) to Incyte, unless specifically requested.

8.5.2 8.5.3 FDA Notification by Sponsor-Investigator

The Columbia University Medical Center Sponsor-Investigator, as holder of the IND, will be responsible for all communication with the FDA. Columbia University Medical Center Principal Investigator will report to the FDA, regardless of the site of occurrence, any adverse event that is serious, unexpected and there is evidence to suggest a causal relationship between the drug and the adverse event. These must be reported to the FDA and any affiliate sites as soon as possible, but in no case later than 15 calendar days after the sponsor determines that the information qualifies for reporting. The Sponsor-Investigator will also submit an IND annual report to the FDA in accordance with 21.CFR 312.33.

The Columbia University Medical Center Sponsor Investigator must report to the FDA and any affiliate site investigators as follows:

- Any unexpected fatal or life-threatening event must be reported as soon as possible, but no later than 7 calendar days after the sponsor investigator initial receipt of the information
- Any findings from epidemiological studies, pooled analysis of multiple studies, or clinical studies, whether or not conducted under an IND, and whether or not conducted by the sponsor-investigator, that suggest a significant risk in humans exposed to the drug must be reported as soon as possible but no later than 15 calendar days after the sponsor-investigator determines that the information qualifies for reporting

- Any findings from animal or in vitro testing whether or not conducted under an IND, and whether or not conducted by the sponsor-investigator, that suggest a significant risk in humans exposed to the drug must be reported as soon as possible but no later than 15 calendar days after the sponsor-investigator determines that the information qualifies for reporting
- Any clinically important increase in the rate of a serious suspected adverse reactions over that listed in the protocol or Investigator Brochure
- Expected SAEs and AEs will be included in the IND Annual Reports

Follow-up information to a safety report should be submitted as soon as the relevant information is available. However, if the results of a sponsor's investigation show that an adverse drug experience not initially determined to be reportable are so reportable, the sponsor investigator must report such experience as soon as possible, but no later than 15 calendar days after the determination is made.

All other serious unexpected experiences associated with the use of the study treatment will be reported to FDA as soon as possible but in no event later than 15 calendar days after initial receipt of the information.

8.5.4 DSMC Reporting by the Sponsor-Investigator

Serious adverse events not constituting unanticipated problems are to be reported to the HICCC DSMC. Reporting should occur within 24 hours of knowledge of the SAE occurring at our institution or affiliate sites.

8.5.5 Reporting to Drug Manufacturer by Sponsor-Investigator

The Sponsor-Investigator will report to the investigational agent manufacturer any serious adverse events that meet the reporting criteria to the Institutional Review Board and/or FDA as described in Section 8.5 within 72 hours of becoming aware of it, so that these reports can be evaluated and included in the Investigator's Brochure and for IND safety submissions per regulations. Reporting will occur by sending the reporting form along with any additional documentation sent to the regulatory authorities.

At the the time of IRB renewal or at the request of the manufacturer, the Sponsor-Investigator will submit a summary of all Serious Adverse Events that have occurred inclusive of all sites to manufacturer.

8.5.5

8.6 **Reporting Process**

Adverse events may be submitted on FDA Form 3500A, the HICCC DSMC Serious Adverse Event Reporting Form, or in a narrative format.

8.7 Reporting of Pregnancy to Incyte

An "Initial Pregnancy Report" or equivalent must be completed in full and emailed to

[contact] or faxed to [name] within 24 hours of discovery of a pregnancy of a subject who has taken the Incyte product or the pregnancy of a partner for a subject who has taken the Incyte product. The "Follow-up Pregnancy Report Form" or equivalent must be completed and emailed to [contact] or faxed to [name] within 30 days after delivery, so that Incyte is provided with information regarding the outcome of the pregnancy. If the pregnancy results in any events which meet the serious criteria (i.e., miscarriage or termination), the SAE reporting process needs to be followed and the timelines associated with a SAE should be followed.

9. STUDY CALENDAR

The screening period for a particular subject commences when the subject undergoes the first study-specific screening assessment. Written informed consent must be obtained before any protocol-specific tests or procedures may be conducted. After informed consent is obtained, baseline evaluations are to be conducted within 2 weeks prior to start of protocol therapy. Routine laboratories – hematology, serum chemistries, and coagulation – performed prior to informed consent may be used if within a 2 week period to start of study treatment. Baseline radiographic evaluations must be done ≤ 4 weeks prior to the start of therapy. In the event that the patient's condition is deteriorating, laboratory evaluations should be repeated within 48 hours prior to initiation of the next cycle of therapy.

9.1 Study calendar

Table 6Trial Flow Chart (Part 2 Only)

Trial Period:	Screening Phase	Treatment Weeks ^a						End of Treatment (last dose) or	Post-Treatment				
Treatment Week:		1	2	3	4	5	6	7	8	Discontinuation	Safety Follow-Up Follow-	Follow-Up	Survival
Scheduling Window (Days):	-28 to -1			Details are de	escribed in the s		(30 days from last dose)	(Q8W)	Pollow-Up (Phone)				
						Administrativ	e Procedures						
Informed Consent ^c	Х												
Inclusion/Exclusion Criteria	X												
Demographics and Medical History	Х												
Prior and Concomitant													
Medication Review	Х			Details are o	lescribed in the s	tudy calendars for	or each agent.			X	Х		
D 1 41	V	F		D (1	(linical Procedu	res/Assessments			X	X	1	F
Events	X			Details are o	lescribed in the s	tudy calendars to	or each agent.	1	1	Х	Х		
12-Lead ECG and echocardiogram ^p	Х												
Physical Examination	Х			Details are o	lescribed in the s	tudy calendars fo	or each agent.			Х			
Ht (V1 only), Wt, &	Х									Х			
Vital Signs (T/P/RR/BP)			Details are described in the study calendars for each agent.										
ECOG Performance Status	X ^m		Details are described in the study calendars for each agent.							Х			
OncoTreat-Prioritized Agent				Details are o	lescribed in the s	tudy calendars fo	or each agent.						
Post-Study Anticancer												v	01200
Therapy Status												X	Q12W
Survival Status						houstowy Duosod	lunes/A seesam on						Q12W
Pregnancy Test -	X	1			La	Doratory Procee	iures/Assessmen				1		1
Urine or Serum β HCG ^d	А												
PT/INR and aPTT ^e	Х												
CBC with Differential ^e	Х		ł	Details are o	lescribed in the s	tudy calendars fo	or each agent.			Х			
Comprehensive Metabolic Papel ^e	Х			Details are o	lescribed in the s	tudy calendars fo	or each agent.			Х			
HBV HCV HIVe,f	x												
1		L				Efficacy Me	asurements			1		1	
Tumor Imaging	Xg					X ^h				Xi			
Tumor markers (CA	Х				,	X ⁿ				X			
19-9 and CEA)e					-								
					Tumor Biopsie	s/Pharmacokine	tics/Correlative	Blood Studies					
Newly Obtained	X ^j				2	Xk				Х			
Tissue Collection													
Pharmacokinetics ^o]	Details are descri	ibed in Section 4 .	8						
(Diood Collection)						V1				v			
(Blood Collection)					1	``				Λ			

- a. Unless otherwise specified, procedures/assessments are to be performed prior to dose administration on Day 1 of each cycle.
- b. Subjects who discontinue study treatment without documented disease progression should continue to be monitored for disease by radiologic imaging every 8 weeks (±7 days) until (1) the start of new anti-cancer treatment, (2) disease progression, (3) death, or (4) the end of the study, whichever occurs first.
- c. Informed consent will include consent for correlative studies including biopsies and serum collections.
- d. For women of reproductive potential, a negative pregnancy test should be performed within 72 hours prior to first dose of trial treatment. Pregnancy tests (serum and/or urine) should be repeated if required by local guidelines.
- e. Laboratory screening tests should be performed within 14 days prior to first dose of study treatment. For all subjects, unresolved abnormal labs resulting in drug-related AEs should be followed until resolution.
- f. All subjects will be tested for HIV, HBV, and HCV prior to enrollment. Those who are positive for HIV, untreated active Hepatitis B, and dual infection with HBV/HCV will be excluded.
- g. Tumor imaging at screening: Imaging will be performed within 28 days prior to the first dose of OncoTreat-prioritized drug. Imaging should include CT chest, abdomen, and pelvis or MRI if CT is clinically contraindicated.
- h. The first on-study tumor imaging will be performed after 8 weeks (±7 days) of treatment and will continue every 8 weeks (±7 days) thereafter (or more frequently if clinically indicated). Timing of imaging follows calendar days and should not be adjusted due to dose interruptions. The same imaging technique, acquisition, and processing parameters for a subject should be used throughout the trial if possible.
- i. Subjects without confirmed PD who discontinue treatment will have imaging performed at the time that study treatment is discontinued (i.e. date of discontinuation ± 4 week window). If a scan was obtained within 4 weeks prior to discontinuation of treatment, then imaging at treatment discontinuation is not required. Subjects who discontinue treatment after confirmed PD will not need further imaging performed during the follow-up period.
- j. Following disease progression/intolerance to standard of care therapy, a fresh tumor biopsy (primary or metastatic site) is required to be performed after the last dose of systemic therapy. OncoTreat analysis will confirm the master regulator profile and the recommended OncoTreat-informed drug.
- k. An optional on-treatment tumor biopsy is requested and will be performed within one month of initiation of an OncoTreat-prioritized drug (28 days ±7 days). The biopsy is to be done within 24 hours of administration of the most recent dose. An optional end-of-treatment tumor biopsy is also requested (±7 days of completing OncoTreat-prioritized drug).
- 1. Collect on Cycle 1 Day 1 and Cycle 2 Day 1 (prior to study treatment administration).
- m. Screening ECOG performance status should be performed within 3 days prior to the first dose of the OncoTreat-prioritized agent.
- n. Serum CA 19-9 will be collected prior to dose administration on Day 1 of each cycle.
- o. On days with PK assessments, patients should not eat breakfast or take the OncoTreat-prioritized agent at home. Upon arrival to the clinic, whole blood will be obtained premorning dose for imatinib and ruxolitinib. Patients will then take the medication as instructed by the clinic staff. For capecitabine, patients will take the medication as instructed by the clinic staff then will have whole blood obtained for PK analysis. See Section 4.8 for details.

Capecitabine: cycle 1 day, cycle 1 day 8

Imatinib: cycle 1 day 2 (24 hours \pm 3 hours after cycle 1 day 1 dose administration)

Ruxolitinib: cycle 1 day 2

p. Baseline transthoracic echocardiogram (TTE) is required for all subjects on the imatinib-treated arm.

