2.3 Exploratory Objectives & Endpoints

2.3.1 Objectives:

The exploratory objectives of this study are to:

- To explore the relationship between drug exposure, pharmacodynamics, efficacy, and safety of each OncoTreat-prioritized agent. Pharmacodynamic response will be evaluated by comparing the master regulator signature of a given subject's tumor using VIPER analysis, comparing pre-treatment and on-treatment tumor samples. The changes in master regulator activity between these two samples will be compared to that predicted from cell-based and PDX-based treatment studies.
- To assess whether the master regulator signature, using VIPER analysis, in a given subject's tumor changes in response to standard-of-care treatment by comparing initial and secondary biopsies collected for each subject before and after one or two lines of systemic therapy (chemotherapy or clinical trial). These data will be used to determine whether the predicted sensitivity of a patient's tumor to the first-or second-line therapy that they receive is predictive of the actual clinical outcomes that are observed during treatment.
- Using the same data as in the bullet point above, assess the frequency with which chemotherapy treatments alter the predicted sensitivity of tumors to other OncoTreat-prioritized agents (p-value $< 1 \ge 10^{-5}$).
- To compare the standard-of-care clinical DNA mutation analysis results with matched master regulator activity profiles to correlate any clinically actionable genomic information with the top OncoTreat-prioritized drugs.
- To evaluate the feasibility of using the OncoTreat technology on peripheral blood circulating tumor cells (CTCs) by comparing master regulators generated from CTCs to those obtained from tumor tissue in matched pre- and on-treatment samples with an OncoTreat-informed agent.
- To identify associations between master regulator profiles and additional clinical, epidemiological, physiological, imaging, or molecular features of the subject or subject's tumor.
- To identify potential biomarkers, beyond the master regulator signature, using additional genomic, RNA, protein, and imaging platforms that are predictive or prognostic of response to each OncoTreat-prioritized agent (p-value $< 1 \times 10^{-5}$).

2.3.2 Endpoints:

Exploratory endpoints of interest include:

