4.3 Study Drugs

4.3.1 Capecitabine

The cycle length will be 21 days, and 1000 mg/m^2 given orally twice per day, usually separated 12 hours apart, on Days 1-14 of a 21-day cycle. Capecitabine should be taken with water within 30 minutes after a meal.

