9.4.4 Eastern Cooperative Oncology Group (ECOG) Performance Status

The investigator or qualified designee will assess ECOG status (Appendix A) at screening, prior to the administration of each dose of trial treatment, and at discontinuation of trial treatment as specified in the Trial Flow Chart (Section 9).

9.4.5 Tumor Imaging and Assessment of Disease

CT chest, abdomen, and pelvis with contrast will be performed at baseline screening, prior to the administration of study drugs, and every 8 weeks thereafter. Subjects will be evaluated for diease response and progression according to RECIST v1.1. Disease status categories include complete response (CR), partial response (PR), stable disease (SD), and progression of disease (PD).

9.4.6 Tumor Tissue Collection, Pharmacokinetics, & Correlative Studies Blood Sampling All patients will have tumor biopsy specimens obtained at baseline prior to study drug administration and then at week 4 (optional) to assess for successful collapse of the master regulator signature in a given patient's tumor. A biopsy will also be requested (optional) at the time of disease progression. Tissue collection, handling, processing, and storage instructions are described in the separate study manual.

Peripheral blood will be collected for pharmacokinetic analysis only during Cycle 1. The timing of blood sampling will vary by study drug (Section 4.8). The exact times of medication administration and the times of these blood samples must be recorded on the appropriate CRF. A validated assay will be used to measure plasma drug concentration. Blood processing, handling, and storage instructions are described in Section 4.8 as well as in the separate study manual.

Peripheral blood will be collected pre-treatment, cycle 1 day 1, and cycle 2 for future evaluation of biomarkers. The analyses may include genomics, transcriptomics, and proteomics. Assessment of ctDNA and OncoTreat analysis on circulating tumor cells (CTCs) may also be performed.

9.4.7 Laboratory Procedures/Assessments

Details regarding specific laboratory procedures/assessments to be performed in this trial are provided below. Laboratory tests for hematology, chemistry, urinalysis, and others are specified in the Trial Flow Chart (Section 9).

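### For capecitabine, the pre-dose Cycle 2 Day 1 correlative blood falls at the end of the drug-free week, so the exploratory on-treatment CTC-tumour comparison mixes dosing states for that agent

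*Combined protocol and SAP*

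**What the plan says.** - **Blood.** Footnote l in section 9.1: "Collect on Cycle 1 Day 1 and Cycle 2 Day 1 (prior to study treatment administration". Section 9.4.6 is looser and gives no day within Cycle 2: "Peripheral blood will be collected pre-treatment, cycle 1 day 1, and cycle 2 for future evaluation of biomarkers". The same section makes the CTC work optional: "Assessment of ctDNA and OncoTreat analysis on circulating tumor cells (CTCs) may also be performed".
- **Capecitabine schedule.** Section 4.3.1: "given orally twice per day, usually separated 12 hours apart, on Days 1-14 of a 21-day cycle". No drug is planned on Days 15-21.
- **On-treatment biopsy.** Footnote k makes it optional and sets two timing rules. The first is "within one month of initiation of an OncoTreat-prioritized drug (28 days ±7 days"). The second is "The biopsy is to be done within 24 hours of administration of the most recent dose".
- **Use of the pair.** Section 2.3.1 evaluates the technology on CTCs by "comparing master regulators generated from CTCs to those obtained from tumor tissue in matched pre- and on-treatment samples with an OncoTreat-informed agent". The listed endpoint (section 2.3.2) is the percentage of prioritized agents that overlap between biopsy and CTCs.
- **Calendars.** Table 7 (capecitabine) marks correlative blood at weeks 1, 4 and 8 and at end of treatment, and tissue at screening, week 5 and end of treatment. Tables 8 and 9 (imatinib, ruxolitinib) mark the on-treatment tissue and the second blood sample in the same column, week 5.

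**The concern.** Footnote l is one rule for three agents with two kinds of schedule. With continuous 28-day dosing, a pre-dose sample on Cycle 2 Day 1 is still an on-treatment sample and sits at the nominal biopsy time. With 14 days on and 7 off, the same rule puts the blood at the end of the rest period, while the 24-hour rule puts the biopsy within a dosing period.

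If CTC and tumour profiles then disagree in a capecitabine subject, two explanations cannot be separated: CTCs do not represent the tumour, or the two samples were taken in different dosing states. Few pairs are expected, so the difference could not be adjusted for afterwards, and a sample not drawn at the right time cannot be recovered. The plan itself treats time since dose as important, because it imposes the 24-hour rule on the biopsy (section 4.1, item 7, and footnote k).

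**Working it through.** The plan gives no figure to reproduce here. The check is calendar arithmetic for an uninterrupted schedule.

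**1. Interval from last dose to blood, capecitabine.** With a 21-day cycle, Cycle 2 Day 1 is study day 22, and the last Cycle 1 dose is on the evening of day 14. Clock times are not in the plan; assume a last dose at 20:00 and a draw at 08:00.

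Interval = (22 - 14) x 24 + 8 - 20 = 180 h.

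- Last dose between 18:00 and 22:00, draw between 07:00 and 11:00: 177 to 185 h.
- Table 7 visit window of 3 days either way: 180 - 72 = 108 h to 180 + 72 = 252 h.

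**2. Biopsy position.** 28 days plus or minus 7 gives study days 21-35 (22-36 if counted from Day 1).

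- Day 21 is a rest day, 7 days after the last dosing day, so it fails the 24-hour rule.
- Days 22-35 are Cycle 2 Days 1-14, all dosing days. A biopsy on day 22 meets the 24-hour rule only after that day's dose.
- Day 36 is a rest day and could qualify only within 24 h of the day-35 dose.
- Table 7's week 5 is days 29-35, that is Cycle 2 Days 8-14.

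So a biopsy that meets both rules follows a recent dose, and the pre-dose Cycle 2 Day 1 blood does not.

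**3. Size of the mismatch.** The biopsy is at most 24 h after a dose. The blood interval is at least 108/24 = 4.5 times that limit across the visit window, and nominally 180/24 = 7.5 times.

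**4. The other agents.** A pre-dose sample on Cycle 2 Day 1 is about 24 h after the last once-daily imatinib dose and about 12 h after the last twice-daily ruxolitinib dose. Both subjects are still in continuous dosing.

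**5. Why half-lives do not measure the problem.** Section 4.8.1 gives 34-50 minutes for capecitabine. Then 180 h is 180 x 60/50 = 216 to 180 x 60/34 = 318 half-lives, and 108 h is still 108 x 60/50 = about 130. But 24 h, the biopsy limit, is already 24 x 60/50 = 28.8 to 24 x 60/34 = 42.4. Parent drug could be essentially gone at both samples. What separates them is whether the subject is in a dosing period. The relevant quantity, the persistence of a master-regulator change after dosing stops, is not in the plan.

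**6. Week-8 blood.** Week 8 is days 50-56. Cycle 3 starts on day 43, so these are Cycle 3 Days 8-14, which are dosing days. The draw comes 8 - 5 = 3 weeks after the week-5 biopsy. Footnote l and section 9.4.6 do not list it, and Tables 8 and 9 do not mark it.

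**The case against.** The strongest reply is that Table 7 does provide capecitabine blood in a dosing period, at week 8, and also blood at end of treatment beside an optional end-of-treatment biopsy. That stands against any claim that capecitabine subjects have no blood drawn while on drug. It does not supply the matched pair: week 8 is about three weeks after the biopsy, and the end-of-treatment pair is not the on-treatment one.

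The date mismatch is also not special to capecitabine. The biopsy window runs 7 days either side for every agent while footnote l fixes the blood, so imatinib and ruxolitinib pairs can also differ by days. That is correct; only the difference in dosing state is specific to capecitabine.

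The reach is small. The biopsy is optional, the CTC analysis may or may not be done, and section 12 plans on 9 treated subjects. If the three named agents were used equally (an assumption), about 9/3 = 3 would receive capecitabine, and fewer would accept the biopsy. This limits the importance of the point but does not remove it.

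A reader might go further and infer that the drug effect has washed out of the blood, that results are therefore biased toward no change, or that disagreement will be reported as failure of the CTC method. The documents support none of these. They give no duration for the effect, define no blood response endpoint that could be biased in that direction, and state no rule for interpreting disagreement; section 10.9, on exploratory analyses, has a title and no content.

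**Conclusion.** The point holds as a minor one. For capecitabine, the plan's own rules pair blood from the end of the drug-free week (about 180 h after the last dose, range about 108-252 h) with a biopsy at most 24 h after a dose, and call the comparison matched and on-treatment. Any disagreement is confounded with dosing state for this agent. The direction and size of a bias are unknown.

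The 180 h rests on assumed clock times. The range rests on the 3-day window and uninterrupted dosing. The 7.5-fold figure might be taken as a minimum, but it is nominal; the window gives 4.5. The week positions rest on the column layout of Tables 7 to 9.

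The pre-treatment CTC-tumour pair is unaffected, as is the pharmacodynamic endpoint, which uses tumour biopsies only. No primary or secondary endpoint and no sample-size figure changes. Separately, Table 7 on one side and footnote l and section 9.4.6 on the other disagree about the week-8 draw.

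**What to change.** - **Capecitabine subjects who have the on-treatment biopsy:** draw the second correlative blood at the biopsy visit, and record time since last dose for both samples.
- **All other capecitabine subjects:** keep the Cycle 2 Day 1 draw, label it off-drug, and leave it out of the matched on-treatment CTC-tumour comparison.
- **Reconcile** footnote l, Table 7 and section 9.4.6 on which blood draws are planned, including whether week 8 is intended and what it is for. Section 9.4.6 names Cycle 2 without a day, so a draw at a Cycle 2 biopsy is compatible with it.

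The cost is wording in three places, with no added visit and no change to dosing. The downside is that capecitabine subjects with and without the biopsy have different second blood time points, and those with the biopsy lose the Cycle 2 Day 1 time point shared with the other agents. Keeping both draws would avoid that loss at the price of one more blood sample.
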